## 4. INTRODUCTION

### 4.1. Overview of the Disease Under Study

Bempedoic acid (ETC-1002) is an inhibitor of adenosine triphosphate-citrate lyase (ACL) (adenosine triphosphate [ATP] citrate lyase), an enzyme upstream of 3-hydroxy-3-methylglutaryl coenzyme A (HMG-CoA) reductase in the cholesterol biosynthesis pathway. It is an oral first-in-class small molecule designed to lower low-density lipoprotein cholesterol (LDL-C) levels in patients with high cardiovascular (CV) risk unable to meet their treatment goals with currently available lipid-lowering therapies.

Proprotein convertase subtilisin kexin type 9 (PCSK9) reduces LDL receptor recycling to the hepatic surface, thereby limiting removal of LDL particles from the circulation. Monoclonal antibodies neutralize PCSK9 and reduce LDL-C levels when administered alone or in combination with other background therapies.

Elevated LDL-C is a major modifiable risk factor for the development of atherosclerosis and atherosclerotic cardiovascular diseases (ASCVD) ([Sharrett 2001](#)). Despite aggressive interventional and pharmacologic therapies, CV disease is the number 1 cause of death globally ([WHO 2015](#)). An estimated 17.5 million people died from CV diseases in 2012, representing 31% of all global deaths. Of these deaths, an estimated 7.4 million were due to coronary heart disease (CHD) and 6.7 million were due to stroke ([WHO 2015](#)). Cardiovascular disease remains the leading cause of death among Europeans, Americans, and around the world. The Global Burden of Disease study estimated that 29.6% of all deaths worldwide (approximately 15.6 million deaths) were caused by CV disease in 2010, more than all communicable, maternal, neonatal and nutritional disorders combined, and double the number of deaths caused by cancers ([Nichols 2014](#)). In the United States (US), based on 2011 death rate data, more than 2150 Americans die from CV diseases daily, an average of 1 death every 40 seconds. Approximately 155,000 Americans dying from CV disease are less than 65 years of age. In 2011, 34% of deaths due to CV disease occurred prior to the age of 75 years, less than the current 78.7-year average life expectancy ([Mozaffarian 2015](#)). As such new therapies to combat this global public health problem are needed.

Global guidelines recommend lowering of LDL-C to levels below 100 mg/dL and often under 70 mg/dL ([Jacobson 2014](#)) or reduction of  $\geq 50\%$  ([Stone 2013](#)). In order to reach these goals, lipid-lowering therapies are often taken in combination. The combination of bempedoic acid and a PCSK9 inhibitor (PCSK9i) may offer an additional treatment option in the future for physicians.

### 4.2. Background on Bempedoic Acid

[figure not shown]
#### 4.2.1. Mechanism of Action

Bempedoic acid is a first-in-class small molecule inhibitor of ACL, an enzyme upstream of HMG-CoA in the cholesterol biosynthesis pathway. Bempedoic acid is a prodrug that requires activation in liver to ETC-1002-co-enzyme A (ETC-1002-CoA), which mediates competitive

[figure not shown]
inhibition of ACL. Inhibition of ACL by ETC-1002-CoA decreases cholesterol synthesis in liver leading to increased LDL receptor (LDLR) expression and LDL particle clearance from the blood. Therefore, inhibition of ACL by ETC-1002-CoA reduces LDL-C via the same pathway as HMG-CoA reductase inhibition by statins.

[figure not shown]
An important differentiating feature of bempedoic acid is that it does not inhibit cholesterol synthesis in skeletal muscle. In addition to preliminary data suggesting that only minor amounts of bempedoic acid enter skeletal muscle (<5% of systemic exposure), skeletal muscle does not express the enzyme required to activate bempedoic acid to ETC-1002-CoA and inhibit ACL. Therefore, bempedoic acid is not anticipated to mediate the adverse effects associated with inhibition of biological intermediates within the cholesterol biosynthesis pathway in skeletal muscle. The long-term safety of bempedoic acid and its metabolites regarding human skeletal muscle is not yet established.

#### **4.2.2. Nonclinical Experience**

**4.2.3. Previous Human Experience**

#### **4.2.4. Dose Selection**

#### **4.2.5. Background Therapy**

Bempedoic acid in this study is currently being evaluated as an add-on to PCSK9i therapy.

#### **4.2.6. Risk Benefit Summary**

To date, the nonclinical and clinical data indicate that bempedoic acid has a favorable risk-benefit profile. The ability of bempedoic acid to achieve clinically meaningful LDL-C-lowering responses while demonstrating a favorable tolerability profile in a variety of patient populations supports continued development of bempedoic acid, an oral ACL inhibitor, in Phase 3 studies.

Please refer to the most recent IB for additional information regarding previous human experience.

## 5. TRIAL OBJECTIVES AND PURPOSE

### 5.1. Study Objectives

#### 5.1.1. Primary Objective

- To assess the 2-month efficacy of bempedoic acid 180 mg/day vs placebo in the reduction of LDL-C in patients on PCSK9i therapy

#### 5.1.2. Secondary Objectives

- To assess the 1-month efficacy of bempedoic acid 180 mg/day vs placebo in the reduction of LDL-C in patients on PCSK9i therapy
- To evaluate the effect of bempedoic acid 180 mg/day vs placebo on apolipoprotein B (ApoB), non-high-density lipoprotein cholesterol (non-HDL-C), total cholesterol (TC), and high-sensitivity C-reactive protein (hs-CRP) after 1 and 2 months in patients on PCSK9i therapy
- To evaluate the safety and tolerability of bempedoic acid 180 mg/day compared to placebo in patients on PCSK9i therapy

#### 5.1.3. Exploratory Objectives

#### 5.1.4. Primary Endpoint

The primary efficacy endpoint for this study is the percent change from baseline to Month 2 in LDL-C.

#### 5.1.5. Secondary Endpoints

- Percent change from baseline to Month 1 in LDL-C
- Change from baseline to Months 1 and 2 in LDL-C
- Percent change from baseline to Months 1 and 2 in ApoB, non-HDL-C, TC, and hs-CRP
- Safety and tolerability of bempedoic acid in this patient population over 2 months, as assessed by AEs and clinical laboratory values

#### 5.1.6. Exploratory Endpoints

[figure not shown]
## 6. INVESTIGATIONAL PLAN

### 6.1. Overall Study Design

This is a Phase 2, randomized, double-blind, placebo-controlled, parallel group multicenter study that will be conducted at approximately 20 clinical sites in North America. Screening Month -4.5 (Visit S1) will occur approximately 18 weeks prior to randomization. After providing informed consent at Visit S1, patients will stop all background lipid-lowering therapy and lipid-modifying nutritional supplements, if applicable. All patients will return to the clinic on Month -3 (Visit S2). During this visit, patients with an LDL-C value  $\geq 160$  mg/dL (via central or local lab) and triglycerides  $< 500$  mg/dL (via central or local lab) will initiate PCSK9 background therapy (Repatha 420 mg once monthly [QM]). Sites that do not use a local lab may need to bring patients back for another visit to administer PCSK9 background therapy, as a qualifying LDL value is required prior to initiating the 3-month PCSK9i run-in period. No other background lipid-modifying therapy except study provided PCSK9i will be permitted during the trial. After 1 month (at least  $30 \pm 3$  days), patients will return to the clinic for Month -2 (Visit S3) followed by Month -1 (Visit S4)  $30 \pm 3$  days later. During these visits, Repatha will be administered, labs will be collected, and safety assessed. At Visit S4, LDL-C will be checked a second time prior to randomization. Patients with an LDL-C  $\geq 70$  mg/dL (via central lab only) at this visit will qualify for randomization. Patients with LDL-C  $< 70$  mg/dL at Visit S4 will be screen failed and no further PCSK9i therapy will be administered. Day 1 should occur 30 days  $\pm 3$  days after Visit S4, once LDL-C eligibility is established. On Day 1, qualified patients will be randomized 1:1 to bempedoic acid 180 mg/day (n = 26) or matching placebo (n = 26). Randomized patients will return for clinic visits at Month 1 (Visit T2) and Month 2 (Visit T3). Both study drug and PCSK9i doses will be administered on site during clinic visits after all procedures have been completed.

An independent expert Data Monitoring Committee (DMC) will formally review accumulating unblinded safety and efficacy data across the bempedoic acid program.

**Figure 1. Study 1002-039 Study Design**

## 6.2. Study Hypothesis

The primary hypothesis is that bempedoic acid will result in greater reduction of LDL-C, as defined by the mean percent change from baseline at Month 2, than placebo when used in combination with a PCSK9i in patients with hyperlipidemia.

## 6.3. Study Duration and Period

The duration of treatment will be 26 weeks (1.5-month screening period, a 3-month lipid-stabilization period, and 2-month treatment period).

## 6.4. End of Study

The study will end when the last randomized patient completes the Month 2 visit. The estimated overall duration of the study (first patient first visit [FPFV] to last patient last visit [LPLV]) is approximately 10.5 months.

## 6.5. Number of Patients

The study will enroll approximately 52 adult patients with hyperlipidemia

## 6.6. Patient Identification Numbers

A unique patient identification number will be assigned to each patient by the interactive web response system (IWRS) at the time of informed consent and will be entered on all documentation. If a patient is not eligible to receive treatment, or if a patient discontinues from the study, their patient identification number cannot be assigned to another patient.

#### **6.6.1. Screening and 1 Month PCSK9i Run-in Period**

Screening will occur approximately 18 weeks prior to Day 1 (Visit T1). Eligible patients will return to the clinical site at Month -3 (Visit S2). During this visit, patients with an LDL-C value  $\geq 160$  mg/dL (via central or local lab) and triglycerides  $< 500$  mg/dL (via central or local lab) will initiate study-provided PCSK9i background therapy (Repatha 420 mg QM). No other background lipid-modifying therapy except study provided PCSK9i will be permitted during the trial.

Patients who are deemed not eligible for randomization at any point during screening will be notified by clinical site personnel regarding their eligibility status and considered screen failures. As necessary, for reasons of safety if a patient begins the run-in period but screen fails prior to randomization, the patient may be asked to return to the clinical site for further evaluation and follow-up of AEs.

#### **6.6.2. Randomization and Treatment Period**

Patients who satisfy all entry criteria, complete the 1.5-month screening period and 3-month PCSK9i run-in period, and have an LDL-C  $\geq 70$  mg/dL at S4 will be randomized. Randomization numbers will be assigned via IWRS on Day 1 (Visit T1). Patients will be randomized in a ratio of 1:1 to receive 1 of the following 2 treatments in a double-blind fashion in addition to monthly PCSK9i background therapy:

- Bempedoic acid 180-mg tablet
- Matching placebo tablet

## 7. SELECTION AND WITHDRAWAL OF PATIENTS

### 7.1. Subject Inclusion Criteria

1. Provision of written informed consent must be obtained prior to any study-specific procedure.
2. Age  $\geq 18$  years or legal age of majority depending on regional law, whichever is greater at Month -4.5 (Visit S1)
3. Fasting, calculated LDL-C at screening ( Visit S2)  $\geq 160$  mg/dL and  $\geq 70$  mg/dL at Visit S4  

Note: A single repeat of LDL-C may be completed. For those patients who have a repeat LDL-C, the average of the 2 values will be used to determine eligibility.
4. Men and nonpregnant, nonlactating women. Women must be:
  - a. Naturally postmenopausal defined as  $\geq 1$  year without menses and:
    - $\geq 55$  years, **or**
    - $<55$  years with follicle-stimulating hormone (FSH)  $\geq 40.0$  IU/L; **or**
  - b. Surgically sterile including hysterectomy, bilateral oophorectomy, and/or tubal ligation; **or**
  - c. Women of childbearing potential willing to use 2 acceptable methods of birth control including:
    - oral, implanted, topical or injectable birth control medications
    - placement of an intrauterine device with or without hormones
    - barrier methods including condom or occlusive cap with spermicidal foam or spermicidal jelly
    - vasectomized male partner who is the sole partner for this patient
    - true abstinence: when this is in line with the preferred and usual lifestyle of the subject. (Periodic abstinence [eg, calendar, ovulation, symptothermal, postovulation methods], declaration of abstinence for the duration of a trial, and withdrawal are not acceptable methods of contraception.)

There are no protocol-specific birth control requirements for men with partners who are able to become pregnant.

### 7.2. Subject Exclusion Criteria

Patients who meet any of the following criteria will not be randomized:

1. Homozygous Familial Hypercholesterolemia (HoFH)

2. Total fasting TG  $\geq 500$  mg/dL (5.6 mmol/L) at Month -3 (Visit S2)

Note: A single repeat of TG may be completed prior to initiation of the single-blind Run-in period. For those patients who have a repeat TG, the average of the 2 values will be used to determine eligibility.

3. Renal dysfunction or a glomerulonephropathy defined as either nephritic or nephrotic syndrome, including estimated glomerular filtration rate (eGFR; using central laboratory determined Modification of Diet in Renal Disease [MDRD] formula)  $<30$  mL/min/1.73 m^2 at Month -4.5 (Visit S1)

Note: A single repeat of eGFR may be completed prior to randomization. For those patients who have a repeat eGFR, the average of the 2 values be used to determine eligibility.

4. All patients with known cardiovascular disease (CVD) or peripheral arterial disease (PAD) or cerebrovascular disease (CD)

5. History of type 1 or type 2 diabetes or laboratory evidence of diabetes (fasting blood glucose [FBG]  $\geq 126$  mg/dL or glycosylated hemoglobin, Type A1C (HbA1C)  $>6.5\%$ ) without prior diagnosis of diabetes at Month -4.5 (Visit S1)

6. Uncontrolled hypertension defined as sitting systolic blood pressure (SBP)  $>160$  mmHg or diastolic blood pressure (DBP)  $>100$  mmHg at Month -4.5 (Visit S1)

7. Uncontrolled hypothyroidism, including thyroid-stimulating hormone (TSH)  $>1.5 \times$  the upper limit of normal (ULN) at Month -4.5 (Visit S1)

8. Liver disease or dysfunction, including:

a. Alanine aminotransferase (ALT) and/or aspartate aminotransferase (AST)  $\geq 2.0 \times$  ULN at Month -4.5 (Visit S1).

b. Positive serology for hepatitis B surface antigen (HBsAg) and/or hepatitis C antibodies (HCV-ABVivi) at Month -4.5 (Visit S1).

Note: If total bilirubin (TB)  $\geq 1.2 \times$  ULN, a reflex indirect (unconjugated) bilirubin will be obtained and if consistent with Gilbert's disease, the patient may be enrolled in the study.

Note: At the discretion of the investigator, a single repeat of ALT and/or AST may be completed. For those patients who have a repeat ALT and/or AST, the average of the 2 values will be used to determine eligibility. Also, if test for hepatitis C antibody is positive, but reflexive test for Hepatitis C ribonucleic acid (RNA) is negative, patient can be enrolled.

9. Gastrointestinal conditions or procedures (including weight loss surgery; eg, Lap-Band® or gastric bypass) that may affect drug absorption

10. History of hematologic or coagulation disorders or a hemoglobin (Hgb) level  $<10$  g/dL at Month -4.5 (Visit S1)

11. History of malignancy (except non-metastatic basal or squamous cell carcinoma of the skin and cervical carcinoma in situ)

12. Unexplained creatine kinase (CK)  $>3 \times$  ULN at screening up to randomization (ie, not associated with recent trauma or physically strenuous activity). Patients with an explained CK elevation must have single repeat CK  $\leq 3 \times$  ULN prior to randomization.
13. History within the last 2 years of drug, alcohol, amphetamine and derivatives, or cocaine abuse. Patients taking amphetamine derivatives for medical reasons such as attention deficit disorder or taking prescription opioids or other meds for chronic pain that have been stable, without evidence of abuse prescribed by and under the care of a health care practitioner can be enrolled after evaluation by the Investigator.
14. Blood donation, participation in a clinical study with multiple blood draws, major trauma, blood transfusion, or major surgery with or without blood loss within 30 days prior to randomization
15. Use of any experimental or investigational drugs within 30 days or 5 half-lives, whichever is longer
16. Previous enrollment in an Esperion Phase 3 bempedoic acid (ETC-1002) clinical study
17. Use of a cholesterylester transfer protein (CETP) inhibitor in the last 12 months prior to screening, such as: anacetrapib, dalcetrapib or evacetrapib
18. Use of, or a plan to initiate, these prohibited therapies/supplements during the study:
  - Mipomersen (must be stopped at least 6 months prior to Month -4.5 [Visit S1]),
  - Lomitapide or apheresis therapy (must be stopped at least 3 months prior to Month -4.5 [Visit S1]),
  - Red yeast rice containing products (must be stopped on or before Month -4.5 [Visit S1]),
  - Lipid regulating drugs or supplements (must be stopped on or before Month -4.5 [Visit S1])
19. Planned initiation or changes to the following drugs prior to Month -4.5:
  - Hormone replacement (6 weeks prior to Month -4.5)
  - Thyroid replacement (6 weeks prior to Month -4.5)
  - Obesity medication (3 months prior to Month -4.5)
20. A medical or situational (ie, geographical) finding that in the investigator's opinion may compromise the patient's safety or ability to complete the study
21. Patient is pregnant or breast feeding, or planning to become pregnant during treatment and/ or within 30 days after the end of treatment
22. An employee or contractor of the facility conducting the study, or a family member of the Principal Investigator, Co-Investigator, or Sponsor.
23. Heterozygous familial hypercholesterolemia (HeFH)
24. Concomitant use of a PCSK9 inhibitor (Praluent® [alirocumab] or Repatha® [evolocumab]) at (Visit S1) or prior use within the past 16 weeks of Visit S1

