#### 10.2.1. Screening Month -4.5 (Visit S1)

The screening period will begin with a screening visit that will occur approximately 18 weeks prior to randomization. Visit S1 will allow the Investigator to assess the patient's preliminary eligibility. After the patient provides written informed consent (see [Section 10.1](#)), the patient will undergo the following assessments and procedures at Visit S1:

- Demographics
- Clinically relevant medical history
- Concomitant and prohibited medication review
- Height (cm), weight (kg), body mass index (BMI)
- Vital signs
- Clinical laboratory evaluations:
  - Hematology, blood chemistry, and urinalysis
  - Basic fasting lipids (TC, calculated LDL-C, [REDACTED], non-HDL-C, [REDACTED], and [REDACTED])
  - HbA1C
  - TSH
  - FSH (in appropriate female patients)
  - Serum pregnancy test (on appropriate female patients)
- Serology (including HBsAg, Hepatitis C virus [HCV])

- Review of all inclusion/exclusion criteria that can be assessed at this time
- Conduct diet and exercise counseling
- Contact IWRS to register the patient

Patients who meet all enrollment criteria that can be assessed following review of the S1 central clinical laboratory results (available several days after Visit S1) will be instructed to washout of all lipid-regulating drugs and supplements and to maintain consistent diet and exercise patterns throughout the study. Patients who fail to meet any entry criterion that can be assessed at Visit S1 are considered to be screen failures and are not required to return for additional visits (although a patient can be seen at any time for safety reasons).

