#### **10.2.2. PCSK9i Run-in Month -3 (Visit S2)**

Prior to scheduling Visit S2, review the screening clinical results to evaluate whether the patient continues to meet eligibility criteria.

- If the patient meets eligibility criteria, then schedule the Visit S2 and proceed with the Visit S2 procedures

The patient will undergo the following assessments and procedures at (Visit S2)

- Concomitant and prohibited medication review (ongoing)
- Assess AEs (starting from signing of the informed consent document)
- Physical examination (PE)
- Vital signs
- Basic fasting lipids (TC, calculated LDL-C, [REDACTED], non-HDL-C, [REDACTED], and [REDACTED])
- ApoB and hs-CRP
- First PCSK9i monthly injection. Verification of lipid entry criteria (LDL-C value of >160 mg/dL and triglycerides <500 mg/dL) must be obtained before starting PCSK9i
- Schedule next visit **(S3 has to be at least 30 days ± 3 days from the first dose of PCSK9)**
  - PCSK9i injections must be administered consistently throughout the trial within 30 ± 3 days from the previous dose. Efficacy will vary if the doses are not consistently administered.

Note: Local labs can be used to assess LDL-C and TGs for entry. All other labs must be run via the central lab. If using a central lab or a local lab with a delay in obtaining results, an optional visit to administer PCSK9 may be scheduled. **Patients need to be on Repatha 420 mg for at least 30 days ± 3 days before conducting Visit S3.**

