### 10.2.4. PCSK9 Run-in Month -1 (Visit S4)

One month ( $30 \pm 3$  days) from S3, patients will have their LDL-C evaluated a second time via **central lab only** prior to randomization on Day 1.

The patient will undergo the following assessments and procedures at (Visit S4)

- Concomitant and prohibited medication review (ongoing)
- Assess AEs (starting from signing of the informed consent document)
- Vital signs
- Basic fasting lipids (TC, calculated LDL C, [REDACTED], non-HDL C, [REDACTED], and [REDACTED])
- Schedule next visit Day 1 **(Day 1 should occur  $30 \pm 3$  days after S4, once LDL-C eligibility  $\geq 70$  mg/dL is established)**
- PCSK9i monthly injection must be given at the end of procedures

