### 10.2.5. Treatment Week 0 (Visit T1; Day 1)

Prior to scheduling Visit T1, review S1, S2, S3, and S4 clinical results to evaluate whether the patient continues to meet eligibility criteria.

- If the patient meets eligibility criteria, then schedule the Visit T1 and proceed with the Visit T1 procedures

If the patient has met all inclusion criteria, none of the exclusion criteria, and has been on Repatha 420 mg **for  $30 \pm 3$  days during each month of the PCSK9 run-in period**, the patient may be randomized into the double-blind treatment period. Patients who fail to meet any entry criterion prior to randomization are considered to be screen failures, will not be randomized into a treatment group, and are not required to return for additional visits. Patients are considered randomized once all eligibility criteria are confirmed and a randomization number is obtained by the IWRs on the day of first dose.

The patient will undergo the following assessments and procedures at (Visit T1)

- Concomitant and prohibited medication review (ongoing)
- Assess AEs (starting from signing of the informed consent document)
- Weight
- Vital signs
- Clinical laboratory evaluations:
  - Hematology, blood chemistry, and urinalysis

Note: Urine pregnancy test (for females of childbearing potential)

- Basic fasting lipids (TC, calculated LDL-C, [REDACTED], non-HDL-C, [REDACTED], and [REDACTED])
- ApoB and hs-CRP
- HbA1C

- Predose PK
- Review inclusion/exclusion criteria to establish patient eligibility. **Patient must have an LDL-C  $\geq 70$  mg/dL at S4 before they can be randomized on Day 1.**
- Conduct diet and exercise counseling
- IWRS contact to obtain the patient randomization number and MED ID number for double-blind study drug
- Dispense IMP and provide dosing instructions (35-day supply bottles)
  - **Subject should be randomized and receive IMP within  $30 \pm 3$  days of S4, as soon as the final LDL-C entry criterion is met**
- PCSK9i injection and IMP must be given at the end of procedures
- Schedule next visit

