**Table 3: Clinical Laboratory Parameters (Safety)**

Clinical Laboratory Test	Clinical Laboratory Test
Other Screening Labs 

• Hepatitis B surface antigen (HBsAg), hepatitis C virus (HCV)b

• Serum pregnancy test (only for females of childbearing potential)

• Follicle-stimulating hormone (FSH; Females <55 years and >1 year without menses)

• Urine pregnancy test prior to randomization (for female of child bearing potential)

• Thyroid-stimulating hormone (TSH)

	

a If TB  $\geq 1.2 \times$  ULN, a reflex indirect (unconjugated) bilirubin will be obtained.

b If HCV-AB is positive, a reflex HCV RNA will be performed to rule out active disease.

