#### **11.1.5.3. Sample Collection, Storage, and Shipping**

Clinical laboratory samples will be collected by appropriate clinical site personnel and then shipped according to a separate laboratory manual provided by the Central Laboratory. Samples will be processed by the Central Laboratory, and PK samples will be forwarded to the Bioanalytical Laboratory for analysis.

Blood draws for lipids, [REDACTED], and glucose must meet the criteria listed below. If these criteria have not been met, these blood samples will NOT be collected. If these criteria can be met by rescheduling the clinic visit to occur within 3 days, the lipid, [REDACTED], and/or glucose blood samples will be collected at the rescheduled clinic visit only.

- Blood samples will be drawn after a minimum 10-hour fast (water is allowed)

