## APPENDIX 1. SCHEDULE OF EVENTS (SUBJECT VISIT SCHEDULE)

Visit	Schedule of Events						
	S1 	S2	S3	S4	T1	T2	T3/EOS) 
Month	Month -4.5	Month -3	Month -2	Month -1	Week 0	Month 1	Month 2
Procedure	Day -135	Day -90 ±3	Day -60 ±3	Day -30 ±3	Day 1*	Day 31 ±3	Day 61 ±3
Informed Consent	X						
Enrollment Criteria	X	X	X	X			
Demographics	X						
Medical History	X						
Concomitant Medications	X	X	X	X	X	X	X
Adverse Event Recording		X	X	X	X	X	X
Physical Exam		X					X
Weight 	X				X		X
Height	X						
Vital Signs 	X	X	X	X	X	X	X
Serology 	X						
Serum Pregnancy/FSH 	X						
Urine pregnancy test for women of childbearing potential only					X		
TSH	X						
Clinical Safety Labs 	X				X	X	X
Basic Fasting Lipids 	X	X**	X	X***	X	X	X
ApoB and hs-CRP		X			X	X	X

	Schedule of Events							
	Visit	S1 	S2	S3	S4	T1	T2	T3/EOS) 
Month	Month -4.5	Month -3	Month -2	Month -1	Week 0	Month 1	Month 2	
Procedure	Day	Day -135	Day-90 ±3	Day -60 ±3	Day -30 ±3	Day 1*	Day31 ±3	Day61 ±3
HbA 1C		X				X		X
PK – predose trough						X	X	X
Diet and exercise counseling 	X	X				X	X	X
Establish Patient Eligibility						X		
Randomization						X		
IWRS Contact 	X					X	X	X
PCSK9i administered at site		X	X	X	X	X	X	
Double-blind Drug Dispensing						X	X	
IMP Return/Compliance							X	X
PCSK9i Return/Accountability		X	X	X	X	X	X	

NOTE: For patients who withdraw from study drug treatment, but consent to be followed for safety assessments and return to clinic for these visit, the visits will occur according to the protocol schedule. Safety assessments should include clinical safety and basic lipid laboratories, adverse events (AEs), physical examination (PE), and vital signs. For patients who withdraw from study drug treatment, but consent to be followed for safety assessments by phone, the telephone contacts will occur according the protocol schedule with information regarding current health status and to collect information on AEs (eg, recent procedures, hospitalizations, and if the patient has died, the cause of death). If a patient does not provide consent to be followed for safety assessments per the protocol (either by returning to clinic or by phone), Visit T4 will be considered the End of Study (EOS)/Early Withdrawal from study and no further visits will be scheduled.

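### The CK exclusion runs up to randomization, but the latest scheduled CK likely to be usable for eligibility is 126 to 135 days old; adding CK at Visit S4 cuts this to 27 to 33 days

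*Protocol*

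**What the plan says.** Protocol section 7.2, criterion 12 (also in the synopsis), excludes unexplained CK above 3 x ULN "at screening up to randomization (ie, not associated with recent trauma or physically strenuous activity". An explained elevation needs one repeat at or below 3 x ULN before randomization. The other seven exclusions that rest on a laboratory or serology result (2, 3, 5, 7, 8a, 8b and 10) each name one visit.

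CK belongs to the blood chemistry panel (Protocol Table 3). In Appendix 1 the row "Clinical Safety Labs" is marked at S1, T1, T2 and T3 only, and the SAP's copy of the schedule agrees.

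On T1, section 10.2.5 has the site review S1 to S4 results before scheduling the visit, and then states that "a randomization number is obtained by the IWRs on the day of first dose". Safety samples are "collected by appropriate clinical site personnel and then shipped according to a separate laboratory manual provided by the Central Laboratory" (section 11.1.5.3). Section 10.2.1 describes the S1 "central clinical laboratory results (available several days after Visit S1".

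Two other late eligibility checks have a test placed so that it can be used. At S4 "patients will have their LDL-C evaluated a second time via" the central laboratory, about a month before Day 1. Table 3 lists a "Urine pregnancy test prior to randomization" for women of childbearing potential.

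Some wording points the other way. Footnote 9 of Appendix 1 describes the safety panel as applying to all visits and refers to the laboratory manual for the detailed schedule. Section 11.1.5.1 also places the by-visit laboratory schedule in that manual. Section 6.1 says in general terms that laboratory samples are taken at S3 and S4.

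**The concern.** CK is the only laboratory exclusion whose window extends to randomization, yet no CK is scheduled between the first screening visit and the day of dosing. In that interval patients stop lipid-regulating drugs and receive three monthly Repatha doses. A patient with a normal CK at S1 who later rises above 3 x ULN without symptoms, and who has no unscheduled test, would probably be randomized and dosed before anyone saw the new value.

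What is at stake is a safety screen, not the efficacy result. Muscle events are of special interest in Protocol section 12.3, which calls for close attention to CK. If the T1 value proves to be between 3 and 5 x ULN, section 11.1.5.4 leaves a repeat to the investigator, because the mandatory confirmatory test in section 11.1.5.4.3 starts only above 5 x ULN. The SAP would record the value as a baseline abnormality (sections 5.2.2 and 5.4.3) and could class it as an entry violation (section 5.2.3), but only after dosing.

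**Working it through.** The plan gives no figure on this point to reproduce. The check sets the schedule against the criterion and counts days.

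**Step 1. Scheduled CK before first dose** (Protocol Appendix 1; sections 10.2.1 to 10.2.5; Table 3)

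| Visit | Day | Relevant blood tests listed | CK |
|---|---|---|---|
| S1 | -135 | Chemistry, hematology, lipids, others | Yes |
| S2 | -90 ± 3 | Lipids, ApoB, hs-CRP | No |
| S3 | -60 ± 3 | Lipids | No |
| S4 | -30 ± 3 | Lipids | No |
| T1 | 1 | Chemistry, hematology, lipids, others | Yes, on the dosing day |

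There are two scheduled draws before first dose and none between them.

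**Step 2. Age of the S1 value at first dose.** Sections 6.1 and 10.2.1 give about 18 weeks: 18 x 7 = 126 days. Appendix 1 gives Day -135, about 135 days. The range is 126 to 135 days.

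**Step 3. Can the T1 value be used?** At T1 the sample, the randomization call, dispensing and the first dose all belong to one visit. The sample is shipped to the central laboratory, and S1 results take several days. At S2, where the same kind of delay could hold up a decision, section 10.2.2 provides for it: "If using a central lab or a local lab with a delay in obtaining results, an optional visit" can be arranged for the injection. T1 has no such provision. From this I infer that the T1 CK normally arrives after dosing. The protocol does not say so.

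**Step 4. Effect of a CK at S4.** Section 10.2.4 puts Day 1 at 30 ± 3 days after S4, so an S4 value would be 27 to 33 days old at first dose. The age falls by 126 - 33 = 93 to 135 - 27 = 108 days.

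The documents give no turnaround in days, so I assume 3 to 7:
- S4 result known before Day 1: 27 - 7 = 20 to 33 - 3 = 30 days.
- Repeat drawn when that result arrives, with the same turnaround: 27 - 7 - 7 = 13 to 33 - 3 - 3 = 27 days before Day 1.

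Both results would be available in time under this assumption.

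**Step 5. Interval after T1 as planned.** The next scheduled CK is at T2, Day 31 ± 3. That is 31 - 1 = 30, or 27 to 33 days after T1.

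These figures measure the age of a sample, not risk. The documents give no rate of CK elevation during run-in, so the number of patients affected cannot be calculated.

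**The case against.** **The key step is inferred.** The gap exists only if the T1 CK is not available before randomization. The several-days wording describes S1, and the laboratory manual could provide a faster route. This stands as a limit on the conclusion.

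**Chemistry may be drawn at S2 to S4.** Footnote 9, section 6.1 and the reference to the manual could be read that way. The more natural reading is that they refer to the tests marked for each visit, because the marked row and all three itemised lists omit chemistry. If a site could read them either way, naming the S4 test settles the matter.

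**The criterion does not demand a test at each visit.** Its open window can be read as covering the repeat of an explained elevation and any unscheduled value. That is fair. A reader might infer that criterion 12 cannot be applied at all, or that the plan leads to dosing in breach of it. The documents do not support this. The criterion works for the S1 value and for any unscheduled value. Only a new, symptomless, untested rise escapes it.

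**CK is treated no worse than other safety tests.** eGFR, ALT/AST, TSH and hemoglobin also rest on S1, so the long interval is a feature of the whole design. Footnote 2 of Appendix 1 allows repeat laboratory tests before T1. The difference is that those criteria name S1, while CK's window runs to randomization. The footnote 2 repeats are triggered by an earlier exclusionary value and would not find a new rise.

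**No harm is shown.** Nothing in the documents suggests that CK should rise during run-in. Adverse events are reviewed at S2, S3 and S4, the investigator may exclude under criterion 20, and CK is followed at T1, T2 and T3. This stands, and it keeps the priority low.

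**The remedy only narrows the gap.** This is also correct.

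**Conclusion.** The point holds as a minor, inexpensive improvement to safety screening. As scheduled, the latest planned CK likely to be usable for eligibility is the S1 value, 126 to 135 days old at first dose, although the criterion's window extends to randomization. This rests on two readings: that T1 central-laboratory results take several days, as at S1, and that the marked schedule and visit lists govern over the general wording in footnote 9 and section 6.1. The unseen laboratory manual could alter either.

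A reader might also infer that the muscle-safety results or the primary analysis are compromised. The documents do not support that. The LDL-C analysis does not depend on CK, the T1 draw remains the CK baseline, and no number of affected patients can be given.

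**What to change.** Add CK to the S4 central-laboratory sample already taken for LDL-C. List it in Protocol section 10.2.4, Appendix 1, the SAP's schedule of events and the laboratory manual, and review it with the S4 LDL-C before Day 1. Section 10.2.5 already requires S4 results to be reviewed before T1 is scheduled, so no new decision step is needed. Leave the wording of criterion 12 as it is, so that unscheduled elevations still exclude and its single-repeat clause covers explained S4 values. Leave the 3 x ULN threshold and the T1 baseline unchanged.

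The cost is one analyte on an existing draw and four document edits, with no extra scheduled visit or venepuncture. There may be a few late repeats, or screen failures after the third Repatha dose, which is given at S4. A rise after S4 would still be seen only at T1.

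A mandatory repeat for any T1 CK above 3 x ULN is optional and not part of this fix. It would be a monitoring preference, since the protocol chose a trigger above 5 x ULN.
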